**Hematologic criteria to start the next cycle (applies only to participants without active disease by bone marrow):**

- ANC  $\geq$  1000/mcL
- PLT  $\geq$  50,000/mcL

Participants who do not meet these hematologic criteria (and without active disease by bone marrow) should have the next cycle delayed and CBC monitored at least weekly until ANC is  $\geq$  1000/mcL and PLT  $\geq$  50,000/mcL.

- If hematologic recovery (ANC  $\geq$  1000/mcL and PLT  $\geq$  50,000/mcL) occurs within 2 weeks of achieving remission by bone marrow, continue Inqovi and KPT-8602 at the same dose for the next cycle.
- If hematologic recovery does not occur within 2 weeks of achieving remission by bone marrow, delay Inqovi and KPT-8602 for up to 2 additional weeks and dose-reduce for the next cycle as noted below:

Dose reduction	Inqovi dosage*	KPT-8602 dosage*
First	Continue same dose	Reduce by one dose level
Second	Reduce by one dose level	Reduce by one dose level
Third	Reduce by one dose level	Reduce by one dose level
Fourth	Reduce by one dose level	Permanently discontinue

*\*Once the lowest dose level has been reached for a given drug, if myelosuppression persists, discontinue drug.*

If not resolved within 8 weeks participant will be taken off treatment.

### 3.3.2.2 Toxicity Guidelines

In addition, the tables below show general supportive care and dose modification guidelines for toxicities noted at any point during study treatment (other than the scenarios described above). Dose levels of KPT-8602 and Inqovi for the purposes of toxicity management are as noted in Section 3.3.1.

### 3.3.2.2.1 Hematologic toxicities

Toxicity	Recommended Action*
Thrombocytopenia	
Grade 2 (PLT $\leq$ 75,000/mcL)	
 
Maintain dose of KPT-8602 and Inqovi.
 
Consider dose reduction of any anti-platelet agents.
 
Start PPI.
 

Grade 3 or 4 thrombocytopenia (PLT $\leq$ 50,000/mcL) without bleeding	
 
In cases where there is still significant disease involvement in the bone marrow:             
 
The treating physician, in consultation with the PI, may continue KPT-8602 and Inqovi at the same dose level
 
 
 
Otherwise, the following guidelines should be followed:             
 
Hold KPT-8602 and Inqovi until improves to <math>\leq</math> Grade 2 or baseline.                     
 
If improves to <math>\leq</math> Grade 2 or baseline within 72 hours:                             
 
Resume KPT-8602 and Inqovi at the same dose
 
 
 
If does not improve to <math>\leq</math> Grade 2 or baseline within 72 hours:                             
 
Hold KPT-8602 and Inqovi for the remainder of the current cycle.
 
Reduce KPT-8602 by one dose level with the next cycle
 
Resume Inqovi at the same dose for the next cycle (first occurrence) or reduce Inqovi by one dose level for the next cycle (second or later occurrences)
 
Note: Toxicity must resolve to <math>\leq</math> Grade 2 or baseline before drugs can be resumed
 
 
 
 
 
In addition, the following steps should be taken for all cases:                     
 
Consider initiating a platelet growth factor per institutional guidelines.
 
Monitor platelet counts at least twice weekly and closely monitor for any bleeding signs/symptoms.
 
Transfuse as per institutional guidelines.
 
Consider dose reduction of any anti-platelet agents.
 
Start PPI.
 
 
 
 
 

Grade 3-4 thrombocytopenia (PLT $\leq$ 50,000/mcL) with bleeding	
 
Consider initiating a platelet growth factor per institutional guidelines.
 
Transfuse as per institutional guidelines.
 
Start PPI.
 
Hold KPT-8602 and Inqovi for the remainder of the cycle and until bleeding resolves and platelet count improves to <math>\leq</math> Grade 2 or baseline, then:             
 
Reduce KPT-8602 by one dose level with the next cycle.
 
Resume Inqovi at the same dose for the next cycle (first occurrence) or reduce Inqovi by one dose level with the next cycle (second or later occurrences).
 
 
 

Neutropenia	
Grade 3 neutropenia (ANC $\leq$ 1000/mcL) without fever	
 
Maintain dose of KPT-8602 and Inqovi.
 
Consider use of growth factors per institutional guidelines.
 

Grade 4 neutropenia (ANC $\leq$ 500/mcL) without fever	
 
In cases where there is still significant disease involvement in the bone marrow:             
 
The treating physician, in consultation with the PI, may continue KPT-8602 and Inqovi at the same dose level
 
 
 
Otherwise, the following guidelines should be followed:             
 
Hold KPT-8602 and Inqovi until improves to <math>\leq</math> Grade 3 or baseline.
 
 
 

Toxicity	Recommended Action*
	
 
▪ If improves to <math>\leq</math> Grade 3 or baseline within 72 hours:                     
 
• Resume KPT-8602 and Inqovi at the same dose.
 
 
 
▪ If does not improve to <math>\leq</math> Grade 3 or baseline within 72 hours:                     
 
• Hold KPT-8602 and Inqovi for the remainder of the current cycle.
 
• Reduce KPT-8602 by one dose level with the next cycle.
 
• Resume Inqovi at the same dose for the next cycle (first occurrence) or reduce Inqovi by one dose level for the next cycle (second or later occurrences).
 
• Note: Toxicity must resolve to <math>\leq</math> Grade 3 or baseline before drugs can be resumed
 
 
 
• Consider use of growth factors.
 
• If growth factors are implemented, for participants who achieve neutrophil levels <math>>1000/\text{mcL}</math> for <math>>4</math> weeks, KPT-8602 may be re-escalated with the next cycle of therapy, with frequent monitoring implemented.
 

Grade 3 or 4 neutropenia with fever	
 
• Implement broad-spectrum anti-microbial agents per institutional guidelines.
 
• Consider use of growth factors.
 
• Hold KPT-8602 and Inqovi for the remainder of the cycle and until fever resolves and the participant is clinically stable, then:                     
 
○ Reduce KPT-8602 by one dose level with the next cycle.
 
○ Resume Inqovi at the same dose for the next cycle (first occurrence) or reduce Inqovi by one dose level with the next cycle (second or later occurrences).
 
 
 
• If growth factors are implemented, for participants who achieve neutrophil levels <math>>1000/\text{mcL}</math> for <math>>4</math> weeks, KPT-8602 may be re-escalated with the next cycle of therapy, with frequent monitoring.
 

\*Once the lowest dose level has been reached, if toxicity persists, discontinue drug.

### 3.3.2.2.2 Non-hematologic toxicities

Toxicity	Recommended Action*
Fatigue	
Grade 3	
 
• Interrupt KPT-8602 dosing until fatigue improves to Grade <math>\leq</math> 2 or baseline. Maintain dose of Inqovi.
 
• If fatigue does not improve to Grade <math>\leq</math> 2 or baseline within 7 days despite holding KPT-8602, interrupt Inqovi dosing.
 
• Once improved to Grade <math>\leq</math> 2 or baseline:                     
 
○ If first occurrence: restart KPT-8602 and Inqovi at the same dose.
 
○ If second occurrence: restart KPT-8602 one dose level below and Inqovi at same dose.
 
○ If third or later occurrence: restart both KPT-8602 and Inqovi one dose level below.
 
 
 

Unintentional weight loss and anorexia	
Grade 3	
 
• Interrupt KPT-8602 dosing until weight loss/anorexia resolves to Grade <math>\leq</math> 2 or baseline. Maintain dose of Inqovi.
 

Toxicity	Recommended Action*
	
 
• If weight loss/anorexia does not improve to Grade <math>\leq</math> 2 or baseline within 7 days despite holding KPT-8602, interrupt Inqovi dosing.
 
• Once improved to Grade <math>\leq</math> 2 or baseline and participant is clinically stable:                     
 
◦ If first occurrence: restart KPT-8602 one dose level below and Inqovi at the same dose.
 
◦ If second or later occurrence: restart both KPT-8602 and Inqovi one dose level below.
 
 
 
• Provide supportive care, including high-calorie supplements, as needed.
 

Grade 4 (anorexia only)	
 
• Interrupt KPT-8602 and Inqovi dosing until anorexia resolves to Grade <math>\leq</math> 2 or baseline.
 
• Once improved to Grade <math>\leq</math> 2 or baseline, participant is clinically stable, and any other contributing factors have been addressed: restart both KPT-8602 and Inqovi one dose level below.
 
• If anorexia does not improve to Grade <math>\leq</math> 2 or baseline within 7 days, permanently discontinue treatment.
 

Nausea or vomiting, acute	
Grade 3	
 
• Interrupt KPT-8602 and Inqovi dosing until resolved to Grade <math>\leq</math> 2 or baseline.
 
• Once improved to Grade <math>\leq</math> 2 or baseline and participant is clinically stable:                     
 
◦ If first occurrence and adequate supportive care resulted in improvement to Grade <math>\leq</math> 1 within 3 days: restart KPT-8602 and Inqovi at the current dose
 
◦ If second occurrence or first occurrence not meeting criteria above: restart KPT-8602 one dose level below and Inqovi at same dose.
 
◦ If third occurrence: restart both KPT-8602 and Inqovi one dose level below.
 
 
 

Diarrhea	
Grade 2	
 
• Rule out infectious causes and institute standard anti-diarrheal therapy
 
• After the first occurrence, consider instituting loperamide 2 mg prophylactically approximately 1-2 hours before the administration of KPT-8602 and repeated every 4 hours for the first 12 hours
 
• Reduce KPT-8602 by one dose level until resolved to Grade <math>\leq</math> 1 or baseline, then restart at the current dose level. Maintain Inqovi dose.
 

Grade 3	
 
• Rule out infectious causes and institute standard anti-diarrheal therapy
 
• Institute prophylactic loperamide, as above
 
• Interrupt KPT-8602 and Inqovi until resolved to Grade <math>\leq</math> 1 or baseline.
 
• Once resolved to Grade <math>\leq</math> 1 or baseline:                     
 
◦ If first occurrence: restart KPT-8602 one dose level below and Inqovi at same dose.
 
◦ If second or later occurrence: restart both KPT-8602 and Inqovi one dose level below.
 
◦ If diarrhea stabilizes for at least 4 weeks at Grade <math>\leq</math> 1 or baseline, then the prior dose of KPT-8602 and Inqovi may be resumed at PI discretion.
 
 
 

Grade 4	
 
• Rule out infectious causes and institute standard anti-diarrheal therapy
 
• Institute prophylactic loperamide, as above
 
• Interrupt KPT-8602 and Inqovi until resolved to Grade <math>\leq</math> 1 or baseline.
 
• Once resolved to Grade <math>\leq</math> 1 or baseline: restart both KPT-8602 and Inqovi one dose level below.
 

Hyponatremia	

Toxicity	Recommended Action*
Grade 3 (sodium level 125-129 mmol/L symptomatic; 120-124 mmol/L regardless of symptoms)	

Consider administration of appropriate saline solution and re-measure serum sodium levels. If (corrected) sodium is Grade <math>\leq 1</math> or baseline, then participant may receive standard dose of KPT-8602.

If immediate sodium correction is not successful, skip 1 dose of KPT-8602 and reassess sodium within 48 hours. Resume KPT-8602 dosing when sodium is Grade <math>\leq 1</math> (<math>\geq 129</math> mmol/L) at the same dose level.

Institute salt supplementation 2-3 times per day.

Grade 4 ( $< 120$ mmol/L; life-threatening consequences)	

Correct sodium as per institutional guidelines.

Institute salt supplementation 2-3 times per day.

Hold KPT-8602 until sodium resolved to Grade <math>\leq 1</math> (<math>\geq 129</math> mmol/L) then reduce KPT-8602 dose by 1 level. Sodium should be reassessed after 1 dose of KPT-8602 is skipped (i.e., within 48 hours) and corrective measures implemented.

If serum sodium stabilizes to Grade <math>\leq 1</math> for at least 4 weeks, original dose of KPT-8602 may be resumed.

Other non-hematologic toxicities at least possibly related to study treatmenta	
a Follow standard dose-modifications for Inqovi as noted in the USPI for Inqovi	
Grade 1 or 2	

Maintain dose of KPT-8602.

Initiate standard supportive care per institutional guidelines.

Grade 3	

Interrupt KPT-8602 dosing until resolved to <math>\leq 2</math> or baseline, then reduce by one dose level.

Initiate standard supportive care per institutional guidelines.

Grade 4	

Interrupt KPT-8602 dosing until resolved to <math>\leq 2</math> or baseline, then reduce by two dose levels.

Initiate standard supportive care per institutional guidelines.

*\*Once the lowest dose level has been reached, if toxicity persists, discontinue drug. Exceptions can be made (i.e., dose reduction not required with the next cycle) for the following adverse events which are not considered clinically significant by the PI: isolated values of  $\geq$  Grade 3 alkaline phosphatase elevation, alopecia*

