## Phase I/II Study Schema

### 3.1.1 Dose Limiting Toxicity (DLT)

The DLT evaluation window will be the first 28 days of study treatment. No dose reductions or interruptions are allowed during the DLT observation period.

A DLT is defined as any of the following treatment-related toxicities (based on CTCAE Version 5.0):

- Any Grade 5 toxicity, unless due to underlying disease, disease progression, or accidental injury.
- Any Grade  $\geq 3$  non-hematologic toxicity, except:
  - Grade 3 or 4 isolated electrolyte abnormalities that resolve, with or without intervention, to Grade  $\leq 2$  within 72 hours
  - Grade 3 nausea, vomiting, or diarrhea that does not require/prolong hospitalization, does not require TPN or NGT feeding, and resolves to Grade  $\leq 2$  within 72 hours
  - Grade 3 fatigue, fever, flu-like symptoms, or headache lasting  $\leq 72$  hours
  - Grade 3 laboratory abnormalities that are not associated with organ pathology
  - Direct complications of cytopenia(s) due to active myeloid malignancy, such as:
    - Grade 3 or 4 febrile neutropenia
    - Grade 3 or 4 infection
    - Grade 3 or 4 hypotension explained by sepsis
    - Grade 3 or 4 hemorrhage/bleeding
- Confirmed Hy's law cases, defined as:
  - AT (ALT or AST) elevation  $> 3$  times upper limit of normal (ULN), AND
  - Total bilirubin  $> 2$  times ULN, without initial findings of cholestasis (elevated serum alkaline phosphatase), AND

- No other immediately apparent possible causes of AT elevation and hyperbilirubinemia, including, but not limited to, viral hepatitis, pre-existing chronic or acute liver disease, or the administration of other drug(s) known to be hepatotoxic.
- In the absence of active MDS, hematologic DLTs for each arm include:
  - any Grade  $\geq 4$  decrease ANC or PLTs lasting more than 28 days.
- Any adverse reaction that leads to dose reduction or withdrawal of KPT-8602.

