##### **Non-hematologic criteria to start the next cycle:**

- Serum Cr < 2 mg/dL
- Serum bilirubin < 2 x ULN
- AST or ALT < 2 x ULN
- No active or uncontrolled infection

Participants who do not meet these non-hematologic criteria should have the next cycle delayed and labs monitored at least weekly. Once resolved, study treatment may resume at the same dose for the next cycle. If not resolved within 4 weeks, dose-reduce when participant meets criteria (as

noted above) to start the next cycle as noted below (if not resolved within 8 weeks participant will be taken off treatment):

Dose reduction	Inqovi dosage*	KPT-8602 dosage*
First	Continue same dose	Reduce by one dose level
Second	Reduce by one dose level	Reduce by one dose level
Third	Reduce by one dose level	Reduce by one dose level
Fourth	Reduce by one dose level	Permanently discontinue

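### The hyponatremia restart rule explains Grade ≤1 as ≥129 mmol/L, but the same table puts 129 mmol/L with symptoms in Grade 3

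*Combined protocol and SAP*

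**What the plan says.** The hyponatremia rows of the table in section 3.3.2.2.2 define two grades by sodium value. The first row is headed "Grade 3 (sodium level 125-129 mmol/L symptomatic; 120-124 mmol/L regardless of symptoms". The second is Grade 4, set at below 120 "mmol/L; life-threatening consequences".

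The rows use Grade ≤1 four times as a condition for dosing:

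- Grade 3 row, after immediate correction: if the re-measured sodium is Grade ≤1 or back to baseline, "then participant may receive standard dose of KPT-8602". No number is attached.
- Grade 3 row, after a skipped dose: "Resume KPT-8602 dosing when sodium is Grade" ≤1, with ≥129 mmol/L in brackets, at an unchanged dose level.
- Grade 4 row: "Hold KPT-8602 until sodium resolved to Grade" ≤1, with the same bracket, followed by a reduction of one dose level.
- Grade 4 row, re-escalation: if sodium holds at Grade ≤1 "for at least 4 weeks, original dose of KPT-8602 may be resumed". No number is attached.

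Sections 6.4 and 8.1.4 name CTCAE version 5 as the grading scale. Neither prints sodium limits, and the limits for Grades 1 and 2 appear nowhere in the document.

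**The concern.** A number placed in brackets after a grade tells the reader which laboratory values satisfy that grade. Here the number admits a value that the heading of the Grade 3 row assigns to Grade 3 when symptoms are present. A clinician who works from the grade and one who works from the number would treat the same participant differently.

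This is the threshold for restarting an investigational drug, in the table meant to govern safety. The number is the more permissive of the two, and it is used after Grade 4 events as well as Grade 3.

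**Working it through.** No sample-size or error-rate formula is involved. The check compares the sodium values each part of the table covers, in whole mmol/L, which is how the table prints its bands.

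**Inputs, all from the hyponatremia rows of section 3.3.2.2.2**

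- Grade 4: below 120, that is 119 or less.
- Grade 3 regardless of symptoms: 120 to 124, five values.
- Grade 3 with symptoms: 125 to 129, five values.
- Bracketed equivalent of Grade ≤1: 129 or more.

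**Joins between the graded bands**

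- Grade 4 to Grade 3: 119 then 120. No shared value, no gap.
- Within Grade 3: 124 then 125. No shared value, no gap.

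**Bracket against the Grade 3 bands, participant with symptoms**

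| Sodium (mmol/L) | Grade by row heading | Grade ≤1 met? | Bracket ≥129 met? |
|---|---|---|---|
| 120–128 | 3 | No | No |
| 129 | 3 | No | Yes |
| 130 or more | Outside the printed Grade 3 band | Not printed | Yes |

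The overlap of {120, …, 129} with {129, 130, …} is {129}. That is 1 of the 5 values in the symptomatic band, or 1 of the 10 values in the Grade 3 heading (5 + 5).

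**With the bracket changed to >129**

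The join becomes 129 then 130, with no shared value and no gap. If sodium is reported with decimals, >129 still meets the top of the Grade 3 band without overlap or gap. This shows that >129 removes the clash with Grade 3. It does not show that >129 is the CTCAE limit for Grade ≤1.

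**Does another section settle the value?**

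- Section 3.3.2.1, "Non-hematologic criteria to start the next cycle": creatinine, bilirubin, transaminases and infection are listed, but not sodium.
- Section 3.1.1: the DLT exception covers "Grade 3 or 4 isolated electrolyte abnormalities that resolve, with or without intervention, to Grade" ≤2 within 72 hours. It uses grades only and a different target grade.
- Sections 6.4 and 8.1.4: CTCAE is named, without sodium limits.
- The footnote to the table: its exceptions concern alkaline phosphatase and alopecia.

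None of them resolves the conflict at 129.

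**The case against.** The best reply is that the grade is the operative condition and the bracket only a gloss. A participant at 129 with symptoms is Grade 3 by the row heading, so is not Grade ≤1, and the sentence as a whole does not permit a restart. That reading is right, and it limits the harm. It also concedes that the printed number is wrong, because on that reading the bracket does not describe the grade it follows.

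A second point concerns the correct figure. Without the Grade 1 and 2 limits, the document shows that the bracket and the Grade 3 heading do not fit together, but not which number belongs to Grade ≤1. This stands, and the fix has to be conditional for that reason.

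Third, touching endpoints occur elsewhere. A platelet count of 50,000/mcL and an ANC of 1000/mcL each satisfy the next-cycle criteria in section 3.3.2.1 and also fall in a toxicity row of section 3.3.2.2.1. Those limits belong to separate rules with separate purposes. Here the grade and its supposed equivalent are in one sentence.

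Finally, section 3.3.2.2 describes the tables as guidelines, and both rows carry other safeguards: a skipped dose with reassessment within 48 hours, salt supplementation and, after Grade 4, sodium correction and a dose reduction. These lower the risk further. They do not correct the figure.

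**Conclusion.** The concern holds: the restart threshold is wrong as written, in both the Grade 3 and the Grade 4 rows. It is a minor point.

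The demonstrated effect is confined to participants at exactly 129 mmol/L whose symptoms persist, and it matters only if someone acts on the number and not the grade. How often that would arise is unknown: the document gives no hyponatremia rate, and the event is not among the frequent toxicities listed in sections 1.2.3.2 and 14.1.3. Sample size, the stopping rules, the DLT rules and the response analysis do not depend on it.

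The one-value count assumes sodium is reported in whole mmol/L. Whether 129 without symptoms also conflicts with Grade ≤1 cannot be judged from the document. Confidence is high that the two parts of the table disagree; the replacement figure awaits the CTCAE check.

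**What to change.** The sponsor should first look up the sodium limit for Grade ≤1 in CTCAE version 5.0. If it is compatible, change the bracket from ≥129 mmol/L to >129 mmol/L (≥130 in whole units) in the two restart sentences, those beginning "Resume KPT-8602 dosing when sodium is Grade" and "Hold KPT-8602 until sodium resolved to Grade". If the CTCAE limit differs, print that figure in both places. The two bullets that use the grade without a number need no edit.

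The cost is one figure in two table cells, which can go into the next amendment. With the >129 version, the only clinical downside is a possible slightly longer interruption for a participant at exactly 129.

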### 3.4 ON STUDY ASSESSMENTS/EVALUATIONS

The following describes all tests and procedures to be conducted on the study and during treatment. Assessments will be performed according to the Study Calendar (Section [3.5](#)).

#### 3.4.1 Timing of Procedures

For each time period, consider the following order of assessments:

- Screening:** Refer to Section [2.2](#).
- Baseline:** Baseline assessments to be performed within 7 days prior to initiating study treatment. Tests performed as part of screening do not need to be repeated if they were performed within the specified window prior to initiating treatment.
- Assessment Windows:** All evaluation days, for flexibility around participant schedules, can be performed within -3 days for a new cycle (day 1, cycle 2-beyond); mid-cycle assessments can be performed with a window of +/- 3 days for cycles 2-beyond. The maximum number of days permitted between the last day of the previous cycle and the start of the next cycle is 28 days.

- **Unscheduled Visits:** In the event of an unscheduled/unplanned visit (e.g., additional clinical assessment(s) due to toxicity), the investigator should use the best clinical judgment as to the necessary assessments. In the event that the decision is made to continue treatment, all tests/assessments as required by the next visit on the Study Calendar (Section [3.5](#)) should still be conducted (or repeated) within the applicable windows. If a decision is made to discontinue treatment, the participant should have a post-therapy follow-up with tests/assessments completed (or repeated) within the applicable windows.
- **Disease Progression:** When a participant has disease progression on treatment while being evaluated at the NIH, evaluations should be done within +10 days after diagnosis of progression.
- **End of Treatment Visit:** To be done 30 days (+10 day window) after the last dose of study therapy. If participants are not able to come to the Clinical Center for this visit, they will be contacted by a member of the study team for adverse events and further cancer therapy. In these cases, the physical exam will not be required, and laboratory tests performed outside of the Clinical Center may be collected.
- **Post-therapy Follow-up:** Follow up will occur via phone call every 3 months (+/-2 weeks) for first 24 months, then every 6 months (+/-4 weeks) for 3 years, then annually until the end of study. Outside medical records will be requested along with the phone call for the first follow-up visit only and if clinically indicated at a later point.
- **End of Study:** To occur when all participants have been followed for up to 8 years or have died.
- **Telehealth/Remote Visits:** In instances when participant is not able to come, participant may be contact by phone, email or other NIH approved remote platform used in compliance with local policy, including HRPP Policy 303. Only unscheduled/unplanned visits may be conducted by telehealth. Scheduled timepoint visits must be conducted in-person, therefore collection datapoints will not be affected.

